
Based on the results of this trial, MF is an oral drug that remains an attractive option for combination with other drugs, and for children (< 30Kg), the allometric dosing is a better regimen, both in terms of drug exposure and therapeutic outcome, while maintaining a good safety profile.

Paromomycin (PM) is a broad spectrum aminoglycoside antibiotic effective against a wide range of bacteria and protozoa. It has been extensively studied in Asia, where the 10-day combination of PM with MF is currently one of the treatment options used

Confidential Page 19 of 68

for VL, with a very safe profile and high efficacy of 98% in the phase III trial and also in the effectiveness study in field conditions. The most frequently reported AEs related to PM are injection site pain, transient mild or moderate increases in alanine aminotransferase (ALT), aspartate aminotransferase (AST), alkaline phosphatase, creatinine and bilirubin enzymes, and reversible ototoxicity (Paromomycin Package Insert, 2016).

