4.2. Exclusion criteria

The presence of any of the following will exclude a subject from study enrolment:

Patients who are relapse cases

Confidential Page 27 of 68

- Patients with Para-Kala azar dermal leishmaniasis grade 3
- Patients who have received any anti-leishmanial drugs in the last 6 months
- Patients with severe malnutrition (for children aged <5 years: weight-for-height WHO reference curves by sex, z score <-3; for patients 5-18 years: BMI-for-age WHO reference curves by sex, z score < -3; for adults >18 years: BMI < 16)*
- Patients with positive HIV diagnosis
- Patients with previous history of hypersensitivity reaction or known drug class allergy to any of the study treatments
- Patients with previous history of cardiac arrhythmia or with a clinically significant abnormal ECG
- Patients suffering from a concomitant severe infection such as TB, schistosomiasis or any other serious underlying disease (e.g. cardiac, renal, hepatic) or chronic condition which would preclude evaluation of the patient's response to study medication
- Pregnant or lactating women
- Female patients of child bearing age who do not accept to have a pregnancy test done
 at screening and/or who do not agree to use contraception from treatment period until
 5 months after the end of treatment (see section 15.2)
- Patients with haemoglobin < 5g/dl
- Patient with signs of severe VL according to Investigator's judgement, requiring an indication for AmBisome therapy based on the clinical manifestations (such as jaundice, bleeding, edema) and clinically significant abnormalities in the following laboratory parameters: haemoglobin, WBC, platelets, liver enzymes (ALT and AST), total bilirubin and creatinine
- Patients with pre-existing hearing loss based on audiometry at baseline
- Patients who cannot comply with the planned scheduled visits and procedures of the study protocol

Confidential Page 28 of 68

^{*} Note: for Ethiopia only: Patients with severe malnutrition (for patients 4-18 years: MUAC cut-off based on MUAC-for-height reference table; for patients > 18 years: MUAC < 170 mm)

5. Schedule of events

Protocol Activities and Forms to Be	Screening		Treat		Follow up visits			
Completed	D-7 to D0	D1	D3	D7	D14	D28 (EOT) +1d	D56 +/- 7d	D210 +/- 14d
Consent form & consent for HIV test	X							
Demographic data and medical history	Χ							
Clinical assessment	X	X	X	Х	X	X	X	X
Nutritional status	Χ							
Audiometric test	Χ				X	X		X
HIV test	Χ							X ¹

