7.6. Blinding and procedures for unblinding

This is an un-blinded open label study.

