8.5. Assessment of Safety

Safety of the different treatment regimens will be assessed through routine monitoring of adverse events. At each study visit, the patients will be enquired about current adverse events or any events observed during the period previous to the visit. In addition, evaluation of hematology and blood chemistry parameters, regular measurement of vital signs and physical examinations will be made at scheduled follow-up visit.

Audiometric test will be performed at baseline and on days 14, 28 and 210 for all patients.

ECG will be performed at baseline and on day 14 in all arms, and in addition on days

Confidential Page 45 of 68

7 and 28 in the reference arm SSG/PM. SOPs will be developed to guide investigators on audiometry and ECG assessments.

Urine pregnancy tests will be performed in woman of child-bearing potential at baseline to exclude any pregnancy, and on D28, D56 and D210 visits to monitor eventual unexpected pregnancy.

HIV test will be repeated at the D210 visit only for patients in Gondar and Abdurafi sites, due to high prevalence of HIV/VL co-infected patients (15%) in this specific population.

The frequency and severity of AEs will be described, as well as frequency of SAEs or AEs that lead to treatment discontinuation. See section 8.6 for AE definition and reporting.

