10.7. Safety Analysis

All patients enrolled and who received at least one dose of study medication (mITT set of patients) will be included in the safety analysis (treatment-emergent AEs). The incidence rate of the most pertinent and frequent ADR (> 5%) of each treatment group will be compared and tested. No adjustment for multiplicity will be performed. These results will be used for assessing the benefit risk ratio.

The proportion of patients with SAE and/or AEs leading to treatment discontinuation will be described per System Organ Class (using preferred terms defined by MedDRA), and summarised according to relationship to treatment and severity (CTCAE, version 4.03). In addition, a narrative for each of the SAE and AE leading to treatment discontinuation will be developed describing all aspects of the medical event.

The proportion of patients presenting at least one treatment emergent AE (TEAE) will be presented. All TEAEs will be described per study arm using the same classification as presented above. AEs will be tabulated by severity (CTCAE V4.03), and causality.

Abnormalities of laboratory/procedures results will be tabulated with respect to clinical significance. In addition, shift tables and graphs will be generated to describe the laboratory parameter values over time, per treatment arm.

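### Section 10.7 plans no per-arm summary of audiometric change from baseline or of recovery by day 210, although every patient is tested four times

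*Combined protocol and SAP*

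**What the plan says.** Section 8.5 states "Audiometric test will be performed at baseline and on days 14, 28 and 210 for all patients", and the schedule in section 5 shows the same four tests. Section 1 lists "creatinine and bilirubin enzymes, and reversible ototoxicity" among the frequently reported paromomycin reactions. Section 4.2 excludes "Patients with pre-existing hearing loss based on audiometry at baseline", so each patient starts from a screened baseline test. Section 7.6 states "This is an un-blinded open label study".

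On analysis, section 10.7 says "Abnormalities of laboratory/procedures results will be tabulated with respect to clinical significance". It adds that "shift tables and graphs will be generated to describe the laboratory parameter values over time, per treatment arm". Neither audiometry nor hearing is named in section 10.7. Section 8.5 says an audiometry SOP will be developed, and section 10.2 refers to a statistical analysis plan. Neither is part of the text reviewed.

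**The concern.** The trial collects a within-patient series that could show whether hearing changes on treatment and whether it comes back. The protocol describes paromomycin ototoxicity as reversible, and both compared arms receive paromomycin, for 14 days in arm 1 and 17 days in arm 3. The analysis section nevertheless gives the over-time, per-arm display to laboratory values alone.

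A change in hearing is counted through a label applied by someone who knows the treatment. The label carries no measure of change from the patient's own baseline, and nothing links a day 14 or day 28 finding to the same patient's day 210 test. What is at stake is a usable per-arm description of a named toxicity, taken from tests already being done, many of them in children.

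**Working it through.** The plan states no figure on this point, so there is none to reproduce. The check traces an audiogram through the document.

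1. **Collection.** There are four tests per patient (sections 5 and 8.5). At 170 patients in each of arms 1 and 3 (section 10.1), and assuming full attendance, that is 2 x 170 x 4 = 1,360 audiograms. Of these, 2 x 170 x 3 = 1,020 are after baseline.

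2. **Route A, procedure table (section 10.7).** Abnormal results are split by clinical significance. No hearing measure, definition of change or definition of recovery is given anywhere in the text. The shift-table sentence covers laboratory values only.

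3. **Route B, adverse events.** Section 8.6.1 makes a procedure abnormality an adverse event if it is assessed as clinically significant, and refers to section 8.6.2. The conditions in 8.6.2 are headed and worded for laboratory results. The first of them does include change since screening. Section 8.6.7 records an event once per patient at its maximum severity, with duration and outcome on the CRF. Section 10.7 tabulates events per arm by CTCAE v4.03 severity and by causality. It plans no table of duration or outcome.

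4. **Formal comparison.** Section 10.7 tests only the most pertinent reactions with frequency above 5%. With 170 patients, 8/170 = 4.7% and 9/170 = 5.3%, so an arm needs 9 patients to cross the line. The documents give no hearing rates. For assumed true rates p, the chance that one arm crosses is P(X >= 9), with X ~ Binomial(170, p):

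| Assumed true rate | Chance that one arm exceeds 5% |
|---|---|
| 2% | 0.8% |
| 3% | 7% |
| 5% | 48% |
| 7% | 85% |

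A drug-related hearing change at 2 to 3% would usually be described but not compared between arms.

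5. **What a simple table could deliver.** Exact two-sided 95% limits with 170 patients are as follows. With 0 changes seen, the upper limit is 2.1%. With 5 seen (2.9%), the interval is 1.0% to 6.7%. This is useful descriptive precision.

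6. **Which visits to contrast.** Paromomycin ends on day 14 in arm 1 and day 17 in arm 3. The day 14 audiogram therefore falls on the last dosing day in arm 1 and before the end of dosing in arm 3. At day 28 the time since the last dose is 28 - 14 = 14 days against 28 - 17 = 11 days. At day 210 it is 196 against 193 days. Days 28 and 210 are the fairer contrasts.

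**The case against.** The strongest reply is that hearing is not left out. A clinically significant hearing change is an adverse event, collected to day 210 (section 8.6.6) and graded by CTCAE. It is tabulated per arm by severity and causality. Section 8.6.11 requires follow-up until it resolves or is judged chronic or stable, and related events are followed beyond the trial. Serious events and events leading to discontinuation also get narratives. The first condition in 8.6.2 is already a comparison with screening, so the judgement is not unguided. Audiometry is not an endpoint in section 2.2.2, and the missing detail may sit in the separate statistical analysis plan or the SOP.

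Most of this stands. A reader might infer that hearing will go unreported, and the text does not support that. What remains is narrower. The adverse event route passes through the same open-label judgement, keeps only the worst grade, and has no planned table of outcome or duration. The information for recovery of reported events is collected, but its summary is not planned.

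A reader might also conclude that a count would miss a moderate hearing shift that a test of mean threshold change would find. The documents do not support this. Neither test is planned, no hearing rates or standard deviations are given, and which method does better depends on whether all patients shift slightly or a few shift a lot. The text does not even say that thresholds in decibels are recorded.

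**Conclusion.** The point holds as a gap in section 10.7: no per-arm summary of audiometric change from baseline and none of recovery at day 210. It is a low-cost improvement to a descriptive safety analysis and does not affect the validity of the primary comparison.

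It rests on two readings. First, audiometry counts as a procedure in section 10.7, since nothing else there could cover it. Second, the four tests are meant to monitor paromomycin ototoxicity. That is a fair inference from section 1, but it is not stated. The crossing chances for the 5% rule depend on assumed rates and only illustrate the point.

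Two further inferences should be resisted. The 7% margin is not put in doubt: section 10.6 bases the safety part of its justification on removing the antimonial, not on hearing. Nor is there evidence here of a hearing difference between arms. Both receive paromomycin, and section 1 reports no rise in ototoxicity at the higher daily dose in earlier work.

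**What to change.** Extend the sentence in section 10.7 on shift tables and graphs to audiometry, per arm, from each patient's own baseline to days 14, 28 and 210. Arm 2 would be shown descriptively.

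- Define hearing change in advance. Use CTCAE v4.03 grade or threshold change where thresholds are recorded, and otherwise normal or abnormal, in each case regardless of the clinical-significance label.
- Report the arm 1 minus arm 3 difference in the proportion with new hearing change, with 95% CI, at days 28 and 210.
- Define recovery in advance. Among patients with a change at day 14 or 28, report the number and proportion recovered at day 210 by arm. State how many had no day 210 test, because section 9.1 withdraws patients who receive rescue treatment.
- Keep the clinical-significance and adverse event tables.

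The cost is a few extra descriptive tables from tests already scheduled. If the CRF holds only normal or abnormal, thresholds would need entry from source records where they exist, or the binary version can be used. No visit, dose or clinical rule changes. If the separate statistical analysis plan or the audiometry SOP already specifies these summaries, a cross-reference in section 10.7 is enough.

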10.8. PK Analysis

Initially, a standard two-stage non-compartmental analysis will be performed using the ncappc script in R to derive the following basic descriptive PK parameters for MF and PM in the intensive PK cohort: Cmax, tmax, AUC_{0-last time-point}, AUC_{0-end of treatment} (MF). Groups of children ≤ 12 years and patients > 12 years will be compared with each other. All results will be descriptively compared to historic data of published MF PK and unpublished PM PK data from the region. Subsequently, in a later phase, a population PK approach will be employed to derive better estimates of drug exposure and also to obtain standard primary PK parameters using a structural compartmental model. Using this model, a more sophisticated covariate analysis will be performed to assess the influence of combining both drugs on each other's PK parameters and additionally other time-constant and time-varying patient characteristics. Also sparse MF PK samples from all patients (in contrast to only the intensive cohort) will be included as well in such a population PK analysis. Exact details and procedures of this population PK analysis will be described in a population PK analysis plan. Such a structural population PK model will also allow for better assessment of exposure-response relationships, which will focus on linking individual exposure parameters to initial cure, final cure/relapse and data on parasite levels (both microscopy and qPCR) and potentially other measured markers of clinical improvement in patients.

Confidential Page 58 of 68

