MF was evaluated as monotherapy and in combination with Ambisome in a phase II clinical trial in Kenya and Sudan (LEAP0208, Omollo et al., 2011; Wasunna et al., 2016). None of the treatment regimens reached the predefined acceptable satisfactory efficacy level of > 90% (point estimate) to be taken forward in a Phase III trial to compare with SSG+PM: Ambisome + MF (10 days regimen) showed a cure rate of 77% (95% CI: 64-90%), and MF as monotherapy (28 days regimen) had 72% (95% CI: 60-85%) efficacy at 6 months follow up. Although not statistically significant (study was not powered for this comparison), there was a clear trend of a poorer efficacy in children (7-12y) as compared to adolescents/adults (13-60y) in the trial, especially in the MF monotherapy arm (59.1% vs 86.2%, p = 0.061). The conventional MF dose linearly based on weight (mg/kg), calculated as 2.5 mg/kg/day, did not provide similar drug exposure in children as compared to adults. This is in line with previous published MF PK data from India and Nepal (Dorlo, Huitema, Beijnen, & De Vries, 2012; Ostyn et al., 2014). MF has a long half-life (7 days), and keeps accumulating over the treatment duration to eventually reach steady-state at the 4th week of treatment. In the LEAP0208 study, for 28 days treatment, the mean end-of-treatment MF concentration

Confidential Page 18 of 68

was 22.1 μ g/mL (IQR 16.8-29.1 μ g/mL) vs 30.2 μ g/mL (IQR 24.7-36.3 μ g/mL) (difference 37%, p<0.001), respectively for patients weighing <30 kg vs patients >30 kg.

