5.1 Schedule of PK/PD events - Intensive cohort

40 patients from Kenya and Sudan in each arm 1 and 2 (20 paediatric ≥7 to ≤12 yrs patients and 20 adolescent/adult patients >12 to ≤50 yrs) will be included in the intensive cohort and will have a separate schedule of PK and PD events as described below. Because of discontinuation of arm 2 in protocol v4.0 dated 22 July 2019, the number of patients in arm 2 enrolled in the PK/PD intensive cohort is expected to be probably less than 40.

Protocol Activities and Forms to Be	Screening	Treatment period (day) +/- 1d except for D28							Follow up visits	
Completed	D-7 to D0	D1	D3	D7	D14	D21 ¹	D28 (EOT) +1d		D56 +/- 7d	D210 +/- 14d
Sampling Time-points:										
Blood sample for paromomycin PK ²	X	Х			Х					
Blood sample for miltefosine PK ³	Х	Χ		Х	Х	Χ	Х		X	
Blood sample for PD (qPCR)			Х	Х	X		Х		X ⁴	X ⁴
Sampling Volumes:										
Total EDTA tube blood volume (mL)	4	12	2	4	12	2	4		4	2
Blood volume for hematology (mL)	1		1	1	1		1		1	1
Blood volume for PK plasma (mL)	2	12		2	10	2	2		2	
Blood volume for PD qRT-PCR (mL)	1		1	1	1		1		1	1
Total dried tube blood volume (for biochemistry)	2		2	2	2		2			2
TOTAL BLOOD VOLUME (mL) 5	6	12	4	6	14	2	6		4	4

¹ D21 visit will only be applicable to the subset of patients allocated to intensive PK sampling in arm 2 (collection of this sample is not applicable anymore in this protocol version).

In order to minimize blood volume collected, a subset of patients will be randomly allocated to one sparse PK sampling schedule:

- D1: either 1, 2, 4, 24h or 1, 2, 8, 24h
- D14: either 0, 1, 2, 4, 24h or 0, 1, 2, 8, 24h

The maximum volume to be collected at a study visit will be 14 mL on day 14.

Confidential Page 31 of 68

² PK PM sample at D1 and D14 (arm 1 and 2):

³ PK Miltefosine sample at D1 and D14 will be collected at the same time points as PK PM (according to the sparse sampling scheme the patient is allocated to). 8h sample will be collected always before the 2nd daily dose. PK samples will be collected prior to the morning dose at D7 and D28 (arm 2). D28 (arm 1) and D56 samples will be collected in the morning.

⁴ Blood samples for qPCR will be collected during the follow-up period (at D56 and D210) only if clinically indicated (i.e. anytime if suspect of relapse, with reappearance of symptoms and signs of VL).

⁵Volume of blood to be collected will be minimized as much as possible, according to the volume of tubes available in the market.

6. Enrolment procedures

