7.2. Doses and treatment regimens

7.2.1 Test arms

Arm 1: Paromomycin 20 mg/kg/d IM q.d. for 14 days combined with oral miltefosine allometric dosing b.i.d. for 14 days

Arm 2: Paromomycin 20 mg/kg/d IM q.d. for 14 days combined with oral miltefosine allometric dosing b.i.d. for 28 days (recruitment is now discontinued in this arm)

MF dosing will be defined as follows:

- Patients <30 kg: the allometric MF daily dose will be calculated according to subject's weight, height and sex
- Patients ≥ 30 to <45 kg: 100 mg/day
- Patients ≥ 45 kg: 150 mg/day

PM and MF will be administered together, both starting at D1. PM dosage will be 20 mg/kg/d for 14 days administered intramuscularly, whereas MF allometric dose will be administered orally for 14 days in arm 1 (it used to be administered for 28 days in arm 2).

Patients are hospitalized for 14 days of PM and MF treatment in both arm 1 and arm 2. The MF treatment will start at the same time as the PM treatment and for arm 2 it used to continue on an out-patient basis until completion of the 28 days treatment.

Miltefosine administration

MF will be administered orally for 14 days in arm 1 and used to be administered for 28 days in arm 2.

Confidential Page 33 of 68

For patients less than 30 kg, the allometric dose will be defined according to weight, height and sex as indicated in Table 1, divided in 2 administrations per day for 14 days in arm 1 or 28 days in arm 2 (not applicable now recruitment has been discontinued in arm 2).

Table 1 - Daily allometric miltefosine dose for female children based on fat-free mass

FEMALE									
HT (cm)	80-89	90-99	100-109	110-119	120-129	130-139	140-149	150-159	160
WT (kg)									
7									
8	30								
9	30			RISK (OF SF\	/FRF N	ΛΑΙ ΝΙ	JTRITI	ON
10		40		111011		THE WHO F			
10	30	40	40		KEFEK IU	THE WHO F	KEFEKENCE	CURVES	
	40		40 40						
12 13	40 40	40 40	40						
14	40	40	40	50					
15	40	40	50	50					
16	40	50	50	50					
17	40	50	50	50	50				
18	50	50	50	50	60				
19	50	50	50	60	60				
20	50	50	50	60	60				
21	50	50	60	60	60	60			
22	50	50	60	60	60				
23	50	50	60	60	60		70		
24	50	50	60	60	60	70	70		
25	50	60	60	60	70		70		
26	50	60	60	60	70		70	70	
27	50	60	60	70	70		70	80	
28	50	60	60	70	70	70	80	80	
29	50	60	60	70	70		80	80	
30	50	60	60	70	70	80	80	80	80

Confidential Page 34 of 68

Table 2 - Daily allometric miltefosine dose for male children based on fat-free mass

MALE									
HT (cm)	80-89	90-99	100-109	110-119	120-129	130-139	140-149	150-159	160

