8.4. Pharmacokinetics and Pharmacodynamics Assessments

8.4.1. Pharmacokinetic Assessments

Patients in arm 1 will have pharmacokinetics measurement of MF at D14, whereas all patients in arm 1 and 2 will have PK measurement of MF at D28 and D56 in order to verify adherence to the treatment.

In addition, intensive sampling for both PM and MF PK will be performed in a subset of patients defined as the intensive cohort: originally 40 in each MF/PM combination arms, with selection of 20 pediatric (≤12 yrs) patients and 20 adolescent/adult patients (>12 to ≤50 yrs). Because arm 2 is discontinued, the number of patients enrolled in this arm in the PK/PD intensive cohort will most probably not reach 40, however samples collected will still be analysed. Enrollment in this intensive cohort will be limited to specific sites located in Sudan and Kenya and as far as possible should be balanced between the two countries. MSF sites will not participate to the enrollment in the intensive PK/PD cohort. These sites will be selected based on their experience, equipment and resources available. Since previous trials (LEAP0714 and LEAP0208) have raised questions on both the (reduced) absorption rate, but also extent of absorption (bioavailability), of MF in East African VL patients, denser sampling is required in this trial than previously performed for MF pharmacokinetics. Due to the PK nonlinearities observed in pediatric patients receiving the allometric MF dosing (LEAP0714), the inclusion of children in this PK sub-study is important and therefore the aim is to have equal numbers of patients below 12 years and above 12 years included in the PK sub-study, to allow for comparison. For PM, we have included a sparse sampling scheme to enable assessment of pharmacokinetic profiles, with subsequent use of population PK modelling to analyze the data. PM PK will be assessed on both day 1 and day 14 of treatment to assess the influence of changing patient characteristics during the treatment period (e.g. increasing body weight, reduced liver damage, etc.) on the PK of PM and to assess potential accumulation of the drug during the treatment period.

Confidential Page 43 of 68

In order to avoid multiple blood sampling in young children, only children from 7 years of age and weighing more than 20 kg will be included in the PK intensive cohort.

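### Miltefosine exposure is compared only by age (12 years) in the first PK stage, while the dosing rule changes at 30 kg; a weight comparison should be added

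*Combined protocol and SAP*

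**What the plan says.** **Analysis (section 10.8).** The first step is a non-compartmental analysis in the intensive cohort. Its only named group contrast is by age: "Groups of children ≤ 12 years and patients > 12 years will be compared with each other". Results are also set descriptively against historic data. A population PK model follows in a later phase. It adds the sparse miltefosine samples from all patients and examines patient characteristics as covariates. Weight and fat-free mass are not named, and the details are left to a separate population PK plan.

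**Recruitment to the cohort.** Section 5.1 sets the composition in each miltefosine/paromomycin arm: "20 paediatric ≥7 to ≤12 yrs patients and 20 adolescent/adult patients >12 to ≤50 yrs" (fewer expected in arm 2). Section 8.4.1 gives the purpose: "equal numbers of patients below 12 years and above 12 years included in the PK sub-study, to allow for comparison". It also sets a floor: "only children from 7 years of age and weighing more than 20 kg will be included in the PK intensive cohort".

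**Dosing (section 7.2.1).** The rule depends on weight, not age: "Patients <30 kg: the allometric MF daily dose will be calculated according to subject's weight, height and sex", then "Patients ≥ 30 to <45 kg: 100 mg/day", and 150 mg/day from 45 kg.

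**Motivation (section 1).** Mean end-of-treatment concentrations of 22.1 and 30.2 µg/mL in the earlier 28-day trial are given "respectively for patients weighing <30 kg vs patients >30 kg". After the paediatric allometric trial, the section concludes that "for children (< 30Kg), the allometric dosing is a better regimen".

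**The concern.** The allometric table is meant to bring patients below 30 kg up to the exposure of heavier patients on the conventional dose. Section 1 says this is unsettled: in the earlier paediatric trial, total exposure rose by 12% but did not reach the adult level. Arm 1 also gives miltefosine for 14 days instead of 28.

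The first-stage comparison uses age in place of a dosing rule that is itself recorded. A child of 12 or under weighing 30 kg or more takes a fixed-band dose but counts as paediatric. A patient over 12 weighing less than 30 kg takes the table dose but counts with the adolescents and adults. Both kinds of crossover pull the two age means together. A gap that remains below 30 kg would therefore look smaller than it is, and the error would be in the reassuring direction.

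**Working it through.** **1. The plan's own figure.** Section 1 states a 37% difference between 22.1 µg/mL (<30 kg) and 30.2 µg/mL (>30 kg). Check: 30.2 / 22.1 − 1 = 36.7%, which agrees. The absolute gap is 30.2 − 22.1 = 8.1 µg/mL.

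**2. Does the dose step at 30 kg in the documents?** Table 1 gives a 29 kg girl of 120–129 cm 70 mg/day: 70 / 29 = 2.41 mg/kg. The text rule at 30 kg gives 100 mg/day: 100 / 30 = 3.33 mg/kg. That is 3.33 / 2.41 = 1.38, or 38% more per kg across the boundary. Above it the dose per kg is not constant: 100 / 44 = 2.27 mg/kg near the top of the middle band and 150 / 45 = 3.33 mg/kg at the start of the next.

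**3. Can the groups cross over?** Section 4.2 and the cohort rules set no upper weight limit for children of 12 or under and no 30 kg floor for patients over 12, so crossover is possible both ways. For adults it is limited: BMI below 16 is an exclusion in Kenya and Sudan, where the cohort is recruited, so an adult under 30 kg would have to be shorter than √(30 / 16) = 1.37 m. Crossover in the older group would come mainly from ages 13 to 18.

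**4. What the age contrast keeps.** Let L and H be mean exposure below and from 30 kg, a the share of the ≤12 group at ≥30 kg, and b the share of the >12 group at <30 kg. Assume mean exposure depends only on the weight class.

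- Mean, ≤12 years: (1 − a)L + aH
- Mean, >12 years: (1 − b)H + bL
- Difference: (1 − a − b)(H − L)

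The documents give no weight distribution by age, so a and b are assumed. The section 1 gap is used only to show scale; it comes from 28 days of conventional dosing.

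| a / b (assumed) | Share kept | Means, ≤12 vs >12 (µg/mL) | Gap (µg/mL) | Relative gap |
|---|---|---|---|---|
| 0 / 0 | 100% | 22.10 vs 30.20 | 8.1 | 36.7% |
| 10% / 10% | 80% | 22.91 vs 29.39 | 6.5 | 28.3% |
| 20% / 20% | 60% | 23.72 vs 28.58 | 4.9 | 20.5% |

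**5. What that means with 20 per group.** The plan attaches no test to this comparison, so this is illustration only. Log-scale SDs from the stated interquartile ranges are ln(29.1 / 16.8) / 1.349 = 0.407 and ln(36.3 / 24.7) / 1.349 = 0.285, pooled 0.352. The full gap is ln(30.2 / 22.1) = 0.312. At a two-sided 5% level (assumed), power is Φ(0.312 / (0.352 × √(2/20)) − 1.96) = Φ(0.85) = 80%. With the gap scaled by 1 − a − b and the mixture variance added, it is about 58% at 10%/10% and 35% at 20%/20%.

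**6. Who is absent from the first stage.** Tables 1 and 2 give doses from 8 kg, but the cohort takes only children from 7 years and above 20 kg. The lightest table-dosed patients appear in no first-stage comparison. The section 5 schedule does plan a D14 pre-dose miltefosine sample for all arm 1 patients outside the cohort, and section 5.1 includes a time-zero D14 sample for those inside it.

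**The case against.** The age split is a deliberate choice. Much of the rationale is by age: section 1 reports the efficacy difference for 7–12 against 13–60 years (59.1% vs 86.2%), and the earlier allometric trial enrolled ages 4 to 12 and was compared with history in the same age group. Section 8.4.1 explains the balance around 12 years by the non-linear PK seen in children. The comparison belongs to an initial, descriptive step. The later population model uses all patients and can treat weight as continuous, which answers the question better than any two-group cut. Recruitment of 20 and 20 was designed around age, and a weight split would lose that balance.

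Most of this stands. It is a good reason to keep the age comparison and not to demote it. It does not make a weight summary unnecessary: the population plan comes later, is not part of these documents, and weight is not named for it in section 10.8.

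A reader might go further and infer that each age group does mix the two dosing rules, or that the age comparison cannot show whether allometric dosing closed the gap. The documents support neither. They permit crossover but give no weight-by-age data, and the adult BMI criterion makes a large share under 30 kg in the older group unlikely. With moderate crossover, most of the contrast survives.

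**Conclusion.** The point holds as a misalignment that blurs a secondary, descriptive result. The only named first-stage contrast is by age, the dosing rule and the reported concentration gap are at 30 kg, and no weight comparison is specified. The age contrast keeps 1 − a − b of any gap between dosing rules: 80% or 60% in the two examples, with a and b assumed and exposure taken to depend on weight class alone. The bias is toward similarity.

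Three limits apply. The µg/mL sizes borrow a gap from 28-day conventional dosing and do not predict arm 1. No concurrent group below 30 kg receives the conventional dose, so neither split can isolate the gain from allometric dosing; both rely on heavier patients and on history. The PK objective is to describe profiles, so the primary non-inferiority conclusion is unaffected.

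**What to change.** 1. In section 10.8, keep the age comparison and add a pre-specified descriptive comparison of miltefosine exposure by baseline weight, <30 kg against ≥30 kg, showing the ≥30 to <45 kg and ≥45 kg bands separately because they carry different doses.
2. Run it on the intensive-cohort non-compartmental parameters and on the D14 pre-dose concentration planned for all arm 1 patients, which also covers the children below the cohort's age and weight floor.
3. Do not set D14 values directly against the 28-day end-of-treatment values in section 1, which states that miltefosine accumulates until the fourth week.
4. Name weight or fat-free mass as a covariate in the population PK plan.
5. Reconcile the 30 kg rows of Tables 1 and 2 with the text. Table 1 shows 50 to 80 mg/day and Table 2 shows 60 to 100 mg/day at 30 kg, whereas the text gives 100 mg/day from 30 kg. Until these agree, a patient at the boundary has no unambiguous dosing-rule group.

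The cost is analysis-plan wording and the reconciliation in item 5; weights and samples are already planned. The downside is that the weight groups in the intensive cohort will not be balanced at 20 and 20, so group sizes should be reported with the results.
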